### 15 Calendar Day Written Report

The Sponsor-Investigator will notify the appropriate review division at the FDA, in a written IND Safety Report, of any serious, unexpected AE that is considered reasonably or possibly related to the use of the investigational product.

Written IND Safety reports will include an Analysis of Similar Events in accordance with regulation 21 CFR § 312.32. All safety reports previously filed by the Sponsor-Investigator with the IND concerning similar events will be analyzed and the significance of the new report in light of the previous, similar reports commented on.

Written IND safety reports with Analysis of Similar Events will be submitted to the appropriate review division at the FDA, and the manufacturer of the investigational product within 15 calendar days of first learning of the event, using FDA Form 3500A.

Written IND Safety Reports will be submitted to the IRB(s) of record per IRB Guidelines.

### IND Annual Reports

The Sponsor-Investigator will provide annual reports to the appropriate review division at the FDA within 60 days of the IND's anniversary date, until the IND is withdrawn or terminated.

### **C.9 Risks of Study Drug:**

A review of 25 studies on the safety and efficacy of CBD did not identify significant side effects across a wide range of dosages, including acute and chronic dose regimens, using various modes of administration. [Bergamaschi M.M., et al. 2011] There are no rare but serious side effects reported. The most frequently occurring side effect was somnolence (i.e.drowsiness) (21%). Other side effects, in order of prevalence, include: fatigue (17%), diarrhea (17%), increased appetite (17%), decreased appetite (16%), and weight loss (9%). [Devinsky O, et al. 2014] Other side effects include extrapyramidal symptoms, increased prolactin levels, weight gain increased serum concentrations of antiepileptic drugs and elevated liver function tests .

Table 2 and 3 show the adverse reactions of CBD from the IB (CBD) provided by GW Research Ltd.

**Table 2.** The adverse reactions with a plausible causal relationship to purified CBD solution—reported at a daily maximum of 25 mg/kg/day

Adverse Reactions	Related causality CBD (n=213)
Most frequently (5 to 10%)	

Somnolence	44 (21%)
Fatigue	36 (17%)
Decreased appetite	31 (15%)
Diarrhoea	29 (14%)
Lethargy	12 (6%)
Increased appetite	15 (7%)
Weight increased	12 (6%)
Convulsion	11 (5%)
Weight decreased	10 (5%)
Gait disturbance	10 (5%)
Less frequently (1 to 5%)	
Drug level increased	9 (4%)
Sedation	7 (3%)

**Table 3.** Most frequently adverse reactions of purified CBD reported at 200, 400, and 800 mg/day

Adverse reactions	CBD 200 mg/day (n=7)	CBD 400 mg/day (n=6)	CBD 800 mg/day (n=7)
Diarrhoea	4 (57%)	3 (50%)	5 (71%)
Dyspepsia	0	1 (17%)	1 (14%)
Defaecation urgency	0	0	1 (14%)
Eructation	0	0	1 (14%)
Frequent bowel movements	0	0	1 (14%)
Gastritis	1 (14%)	0	0
Gastrointestinal hypermotility	0	1 (17%)	0
Vomiting	1 (14%)	0	1 (14%)
Fatigue	1 (14%)	1 (17%)	0
Product size issue	1 (14%)	0	0

Aspartate aminotransferase increased	1 (14%)	0	0
Gamma-glutamyltransferase increased	1 (14%)	0	0
Platelet count decreased	1 (14%)	0	0
Decreased appetite	1 (14%)	0	1 (14%)
Dysgeusia	0	0	1 (14%)
Headache	1 (14%)	2 (33%)	0
Pollakiuria	0	0	1 (14%)
Rash generalised	0	0	1 (14%)
Rash maculo-papular	0	0	1 (14%)

Based on data of Epidiolex and previous studies, some side effects, such as diarrhea, weight loss, and decreased appetite, required reduction of the dose resulting in improvement of symptoms. The large majority of adverse events were mild to moderate and transient. No significant laboratory abnormalities were observed.

**D. Description, Risks and Justification of Procedures and Data Collection Tools:**

Patients could be uncomfortable about their survey of cannabis, drug, alcohol and tobacco use that is administered during screening in both Stages. However, this information is essential for their safety, to check for history of addiction. If this is found then subject could be harmed by participating and thus would be excluded. Also this information is needed for scientific rigor. Federal funding sources are likely to want this information to understand the relevance and importance of future cannabis studies. The importance of having the information will be explained and the subject will be reminded that participation is voluntary.

CBD's effect on many aspects of PD are being studied, besides the primary and major secondary outcome measures. This makes the visits longer and may be tiring for some subjects. To minimize discomfort subjects will be offered sufficient breaks and maximal efforts for efficiency will be made to minimize visit time. The reason for the many assessments is twofold. First, PD is a complex disorder with many different disabling symptoms, and secondly, it is prudent to maximize the information from this study. Studies on cannabis are sorely needed, since many PD patients are taking this potentially dangerous drug as it becomes more available. Access is becoming more available throughout the US as more states are considering legalizing use of medical and recreational marijuana. Besides this lack of vital information, obtaining funding and getting through all the regulatory steps required for study of cannabis is very hard, thus we want to obtain maximal information when such a study (as this one) can be done. This information is vital to guide future studies.

To minimize the risk in the study, the following procedures will be complied with:

1. The study will be conducted in compliance with the COMIRB approved protocol, GCP and the applicable regulatory requirements.
2. The study will be overseen by COMIRB and a Data Safety Monitoring Board (DSMB) at University of Colorado.
3. Each patient will be contacted by phone every 3rd or 10th day and the 3rd day following discontinuation of study drug as described in Section C during in both the dose escalation safety study and the RCT to monitor for adverse effects or withdrawal, as well as changes of medical history and concomitant medications. These phone calls will be done by a RN, APP or MD.
4. Adverse events and serious adverse events will be reported from the time of study drug administration until the last study visit or death, whichever occurs first, according to mandated guidelines.
5. All adverse events and serious adverse events will be followed until resolution (or return to baseline status), or until the condition stabilizes or is otherwise explained, or until subject dies or is lost to follow-up.
6. Safety assessments are comprehensive and include vital signs, history & physical examination, concomitant medications collection, EKGs, safety labs, blood and urinary cannabis and metabolites analysis, MoCA, QUIP-RS, C-SSRS, NPI, SCOPA-sleep, Anxiety short form, Depression short form, Emotional and behavioral dyscontrol short form, Fatigue Severity Scale, Pain Intensity and Interference short form, study drug compliance check, adverse event check and urine and blood pregnancy testing.

We will follow the FDA's Guidance for evaluating and monitoring potential drug-induced hepatotoxicity. Subjects with stable liver disease can be included if they have a normal total bilirubin and prothrombin time/INR at baseline. Liver function tests (ALT, AST, ALP and bilirubin) will be drawn at baseline and at each visit while subjects are on study drug. In addition, if these labs are abnormal at the end of study visit they will be repeated at the safety follow up visit two weeks later and repeated until back to baseline values. During each phone call that assesses effects of study drug, nonspecific symptoms of Drug Induced Liver Injury (DILI) will be checked, e.g., anorexia, nausea, fatigue, right upper abdominal discomfort, and vomiting. If symptoms indicative of DILI occur the subject will return to clinic immediately for measurement of laboratory signs of hepatic injury, regardless of when the next visit or monitoring interval is scheduled. At any time if aminotransferase enzymes are greater than 3x upper limit of normal (ULN), we will repeat ALT, AST, ALP and bilirubin within 48-72 hours. If symptoms persist or repeat testing shows aminotransferase >3xULN for subjects with normal baseline measures or 2-fold increases above baseline values for subjects with elevated values before drug exposure, we will initiate close observation to determine whether the abnormalities are improving or worsening. Per the FDA, close observation includes:

- Repeating liver enzyme and serum bilirubin tests two or three times weekly. Frequency of retesting can decrease to once a week or less if abnormalities stabilize or the trial drug has been discontinued and the subject is asymptomatic.
- Obtaining a more detailed history of symptoms and prior or concurrent diseases.
- Obtaining a history of concomitant drug use (including nonprescription medications and herbal and dietary supplement preparations), alcohol use, recreational drug use, and special diets.
- Ruling out acute viral hepatitis types A, B, C, D, and E; autoimmune or alcoholic hepatitis; NASH; hypoxic/ischemic hepatopathy; and biliary tract disease.

- Obtaining a history of exposure to environmental chemical agents.
- Obtaining additional tests to evaluate liver function, as appropriate (e.g., INR, direct bilirubin).
- Considering gastroenterology or hepatology consultations.

We will gather further history as recommended. Unless we find that the repeat testing shows the aminotransferase levels decline to baseline, we will consult the UCH Hepatology team to determine further management.

The FDA advises that since transient fluctuations of ALT or AST are common, and progression to severe liver injury or failure is uncommon, automatic discontinuation of trial drug upon finding a greater than 3xULN elevation of ALT or AST may be unnecessary. The decision of whether to stop study drug will be affected by information on related drugs, the accumulating clinical experience, the clinical status of the patient, and many other factors. We will consult the UCH hepatology service and keep the following FDA guidance in mind. The FDA states that discontinuation of treatment should be considered if:

ALT or AST >8xULN

ALT or AST >5xULN for more than 2 weeks

ALT or AST >3xULN **and** (TBL >2xULN **or** INR >1.5)

ALT or AST >3xULN with the appearance of fatigue, nausea, vomiting, right upper quadrant pain or tenderness, fever, rash, and/or eosinophilia (>5%)

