### Assessment of tolerability of each dose level

Tolerability will be assessed at each dose via collection of adverse events during administration of the standardized phone script by appropriate study staff. Severity of adverse events will be graded according to the Common Terminology Criteria for Adverse Events (CTCAE), which is published by the National Cancer Institute (NCI) of the National Institutes of Health (NIH):

Grade 1: Mild; asymptomatic or mild symptoms; clinical or diagnostic observations only; intervention not indicated.

Grade 2: Moderate; minimal, local or noninvasive intervention indicated; limiting age-appropriate instrumental ADLs. Instrumental ADLs refer to preparing meals, shopping for groceries or clothes, using the telephone, managing money, etc.

Grade 3: Severe or medically significant but not immediately life-threatening; hospitalization or prolongation of hospitalization indicated; disabling; limiting self care ADLs. Self care ADLs refer to bathing, dressing and undressing, feeding self, using the toilet, taking medications, and not bedridden.

Grade 4: Life-threatening consequences; urgent intervention indicated.

Grade 5: Death related to AE.

The protocol for dose adjustments, maintenance and discontinuation based on adverse effects is as follows:

- For subjects with a grade 1 adverse event the dose will be increased by up to 5 mg/kg/day, or if they are on the maximal targeted dose (20 mg/kg/day) it will be continued.
- For subjects with a grade 2 adverse event the dose will be reduced by 5 mg/kg/day or less.
- For subjects with a grade 3 or 4 adverse event that the Investigator determines is unrelated, the dose will be continued. When the adverse event is stabilized or resolved, e.g., subject is stable after a hip fracture repair, the dose will be increased unless they are already on the maximum targeted dose.
- For subjects with a grade 3 or 4 adverse event that the Investigator determines is related the study drug will be stopped and not restarted.

The Investigator will determine relatedness as described in Section IV. C.8, and will consider the adverse event related if she determines there is at least a reasonable possibility.

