The major dose limiting effect, per GW, is somnolence. To monitor for this closely, the daytime sleepiness part to the SCOPA-sleep will be administered during each phone call, thus before each increase in dose. A score of >7 (note that the average score for PD is  $5.2 \pm 4$ ), if greater than before and considered problematic by the appropriate clinical staff, would result in the subject being instructed to drop to the prior dose for three more days before increasing the dose.

Additional assessments of safety and tolerability is done at the study visit when the subject is on the maximum tolerated or targeted dose. The same protocol for dosing is applied for both adverse events found during phone assessments and during study visits.

The results of safety and tolerability assessments in Stage 1 will be studied to determine if additional evaluations during Stage 2 are warranted. For example, if grade 1 or 2 adverse events occur in  $\geq 2$  subjects then additional surveillance will be conducted during Stage 2. Further, safety and tolerability Stage 1 results determine participant and study stopping parameters, described in Section IV C.7.

The CTCAE criteria are used to determine dose level adjustments and for participant and study stopping rules (Section IV C.7). Adverse events for both Stage 1 and 2 will be collected and reported as discussed in Section IV C.8.

To mitigate potential risk during the study, the subjects will be told not to drive cars or operate dangerous machinery while taking study drug in the Open Label Dose Escalation Tolerability study (Stage 1). Instructions to subjects in the Randomized Controlled Trial (Stage 2) will be developed after Stage 1 is completed, with COMIRB guidance.

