### **Participant stopping rules (Both Stages):**

- If subject cannot tolerate the study drug at any dose level
- if subject develops a CTCAE criteria grade 3 or 4 adverse event per that the Investigator determines is related the study drug
- Pregnancy or breast-feeding
- Requested by subject to terminate treatment
- Failure by the subject to attend consecutive study visits;
- Subject is at significant risk of failing to comply with the provisions of the protocol as to cause harm to self or seriously interfere with the validity of the study results;
- At the discretion of the IRB, Food and Drug Administration (FDA).

If a subject is withdrawn from the study, all efforts will be made to complete the early termination visit that includes efficacy assessments and safety follow-up. In addition, women of childbearing potential will have a post-study pregnancy test performed at the early termination visit.

Withdrawals and the reason for withdrawal will be tabulated by treatment group. The number and percentage of subjects who complete the study will be summarized by treatment group. The number and percentage of subjects who withdraw from the study will be tabulated by original treatment group and last treatment taken at time of withdrawal. Study medication discontinuations will be summarized in a similar fashion.

Subjects will be advised that they are free to withdraw from the study at any time. Reasons that subjects may be withdrawn from the study include the following:

Subject discontinued study medication and wishes to withdraw.

Subject consent is withdrawn.

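### A related grade 3 or 4 ALT/AST rise above 3×ULN must stop study drug under Sections IV.C.2 and IV.C.7, while Section IV.D leaves stopping to judgement, and no precedence is stated

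*Combined protocol and SAP*

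**What the plan says.** Three places in the combined protocol and SAP bear on the same decision.

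- **Section IV.C.2, Assessment of tolerability of each dose level.** For a "grade 3 or 4 adverse event that the Investigator determines is related the study drug will be stopped and not restarted". The section adds that "The CTCAE criteria are used to determine dose level adjustments and for participant and study stopping rules", and that "The same protocol for dosing is applied for both adverse events found during phone assessments and during study visits".
- **Section IV.C.7, Participant stopping rules (Both Stages).** A participant stops "if subject develops a CTCAE criteria grade 3 or 4 adverse event per that the Investigator determines is related the study drug". The bar on restarting is not repeated here; the section goes on to describe withdrawal.
- **Section IV.D, liver-injury monitoring.** After ALT or AST exceeds 3×ULN the plan is to retest, observe closely and consult hepatology unless values return to baseline. It relays FDA advice that such a rise need not lead to stopping automatically. It then says "The decision of whether to stop study drug will be affected by information on related drugs", along with accumulating experience, the patient's clinical status and other factors. Its list of severe patterns, which includes ALT or AST above 8×ULN, and above 3×ULN with total bilirubin above 2×ULN or INR above 1.5, is introduced by "The FDA states that discontinuation of treatment should be considered if".

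Section D mentions neither CTCAE grade nor C.7. Sections C.2 and C.7 do not mention D.

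**The concern.** Liver injury has its own monitoring section, prompts several medication exclusions and is the reason for the acetaminophen limit. Staff facing a marked enzyme rise need one answer on whether dosing ends, and the protocol gives two. Two subjects with the same related rise could be handled differently, each in line with a section of the protocol, depending on which section the investigator consults.

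Subject safety comes first. The inconsistency also reaches a primary measure in both stages, the share of subjects who leave because they cannot tolerate study drug, and the withdrawal tabulation in C.7. In the Stage 2 crossover, a subject stopped in the first phase receives no second-phase treatment. That subject then has no change score between periods for the two-sample t-test in Section F.

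**Working it through.** The main check is a comparison of texts. The only arithmetic concerns what one case would do to the dropout proportion.

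| | C.2 | C.7 | D |
|---|---|---|---|
| Trigger | Grade 3 or 4, related | Grade 3 or 4, related | ALT or AST above 3×ULN, no upper limit |
| Action | Stop, no restart | Stop | Judgement, with hepatology consult |
| Liver or laboratory exemption | None | None | Not applicable |
| Precedence stated | No | No | No |

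**Step 1. Do enzyme rises count as adverse events under C.2 and C.7?** Nothing excludes them. C.2 applies its dosing rules to events found at study visits, and D has liver tests drawn at visits on study drug. C.8 refers to abnormal laboratory values alongside adverse events. Table 3 in C.9 lists raised AST as an adverse reaction (1 of 7, 14%, at 200 mg/day).

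**Step 2. Do the triggers overlap?** Let g×ULN be the ALT/AST level at which grade 3 begins. The documents do not give g. D starts at 3×ULN and has no ceiling, so the overlap is every related rise above max(3, g)×ULN. That range is not empty, whatever g is. The printed generic definition, "Grade 3: Severe or medically significant but not immediately life-threatening", gives a second route: it also covers events for which hospitalization is indicated. A related rise above 3×ULN of that kind is grade 3 and still falls under D.

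**Step 3. How easily is a rise judged related?** C.2 asks only for a reasonable possibility. C.8 makes an event related unless one of three listed exclusions applies. An unexplained rise would tend to count as related.

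**Step 4. Which actions comply?**

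- Stopping for good complies with all three sections.
- Continuing is open under D but breaches C.2 and C.7.
- Restarting after recovery is not excluded by D. It breaches C.2 explicitly, and it does not fit C.7, which treats the event as a reason to stop the participant.

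**Step 5. When would the choice arise?** In the Stage 1 schedule the metabolic profile is done at screening, at Visit 3 and, conditionally, at safety follow-up. The dose is zero in the columns after Visit 3, so the one scheduled on-drug result arrives as dosing ends. Only a symptom-prompted test under D could raise the question earlier. In Stage 2, C.3 has blood drawn at the low-dose visits (3 and 7) and the 20 mg/kg/day visits (4 and 8). That is 2 visits × 2 phases = 4 scheduled tests with dosing in that phase still to come. Visit 5 also counts, because the second phase lies ahead.

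**Step 6. What does one case change?** Assume a subject stopped under C.7 is counted as an intolerance dropout and one continued under D is not. The shift is 1/n.

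- Stage 1: up to 20 subjects are recruited to end with 10. If the dropout is replaced, n runs from 11 to 20, so the shift is 1/11 = 9.1 points down to 1/20 = 5.0 points.
- Stage 2: up to 60 are recruited to end with 50. The shift is 1/50 = 2.0 points down to 1/60 = 1.7 points.

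**The case against.** The best defence is that the sections can be read together. C.7 could be a floor for related grade 3 or 4 events, with D adding liver-specific triggers below it. Or D could govern the work-up period: repeat testing within 48–72 hours and exclusion of viral, autoimmune, alcoholic and biliary causes may reveal an alternative explanation, which makes the event unrelated under C.8. Both readings are sensible, but the protocol states neither. A reader who lets the specific liver section override the general rule reaches the other answer with equal warrant. D's listed factors bear on whether to stop, and it gives relatedness no stated role.

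Several limits on the point do stand, and they rule out stronger inferences that a reader might draw.

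- *That the rules are opposite.* They are not. One is mandatory and the other discretionary, and D never directs that dosing continue.
- *That any liver-enzyme rise is affected.* D's text on not stopping automatically concerns values above 3×ULN, and lower-grade or unrelated rises never meet C.2 or C.7. On the printed grades alone, an isolated asymptomatic rise could even be read as grade 1, because that grade covers findings that are only diagnostic. Grading by enzyme level needs the CTCAE laboratory table, which the protocol does not reproduce.
- *That Stage 1 dose-finding is at risk.* Step 5 shows that the scheduled Stage 1 result comes too late to change a maximal tolerated dose. Only symptom-prompted tests could.
- *That one Stage 1 case is worth 10 points.* That takes 10 as the denominator and ignores recruitment of up to 20.
- *That the study stopping rule is distorted.* C.7 counts related events of grade 3 or above in two or more subjects. That count depends on grade and relatedness, not on whether dosing continued.

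Such cases may also be rare. C.1 cites an open-label epilepsy study with hepatotoxicity below 1%, only in subjects on valproate, which is excluded here. But that population had a mean age of 10, and no CTCAE grades are given.

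**Conclusion.** The inconsistency is real but narrow. It applies to an ALT or AST rise above 3×ULN that is also CTCAE grade 3 or 4 and judged related. For that event C.2 and C.7 require stopping, D permits continuing, and nothing ranks them.

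The conclusion assumes only that some rises above 3×ULN are graded 3 or 4 and judged related; no outside cut-off is needed. The level at which the overlap begins and the number of subjects it would affect cannot be given from the documents. Practical exposure lies mainly in Stage 2, where one case is worth about 2 percentage points on the intolerance dropout measure. In Stage 1 it is confined to symptom-prompted tests, at 5 to 9 points per case. Because this is a safety stopping rule and easy to repair, it should be corrected even if few subjects are ever affected.

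**What to change.** Reconcile C.2, C.7 and D. State in one place which rule governs a related liver-enzyme elevation that also meets CTCAE grade 3 or 4, including whether restarting is possible, and cross-refer from the other two sections. Which rule applies is a clinical choice for the sponsor and its clinicians; this review takes no position on it.

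The cost is one sentence and two cross-references in a protocol amendment. Sample size, visit schedule and analysis are unchanged.
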